**The investigator must inform JSC BIOCAD within 24 h about the patient's premature withdrawal and specify the reason.**

If the subject discontinues the study, an Early Withdrawal Form should be filled out in the CRF. The follow-up procedures for the discontinued subjects are described in section 5.4 *Procedures by Visits*.

Patients who discontinue the study will not be replaced.

For further details see Section 11.6. *Study termination*.

#### **4.9. Drug accountability**

The investigator is responsible for the test drug/placebo accountability at the trial site. Throughout the study, the investigator must ensure proper accountability of the investigational product as required by regulatory authorities. The investigator must maintain accurate records regarding the receipt of the investigational product from JSC BIOCAD, its dispensing to study subjects and return to JSC BIOCAD.

The amount of investigational product delivered to the study site must be recorded in the receipt form provided by JSC BIOCAD. This form will be used as an investigational product accountability record.

Drug accountability records must be available to the CRA during each monitoring visit.

Accounting records should include:

- Delivery confirmation;
- Inventory at the study site;
- Use of the investigational products by each study subject;
- Return of unused drug product to JSC BIOCAD.

Records should include dates, amounts, batch numbers, and expiry dates of the investigational product (if applicable). The investigator must maintain accountability records to ensure that:

- Study subjects get the investigational product at doses specified by the Protocol/Amendment provided by JSC BIOCAD; Unused investigational product is not used for any other purpose except this study.

The CRA from JSC BIOCAD will regularly inspect drug accountability records.

The patient will return used syringes in a special container and cardboard cartons (secondary packaging) at every visit. The investigator should check the amount of the investigational product used.

#### **4.9.1. Handling of the investigational products**

The investigational product will be delivered to the study site before the study start (before the inclusion of the first patient). All packs will have a “For clinical studies” label.

At the study site, the investigational product must be stored at 2 to 8 °C, protected from light, in a limited access area. Access to the storage area will be granted only to the Principal Investigator, co-investigators, members of the study team, and an authorized representative of the site administration who has access to the storage area granted by the local regulations. The investigator must maintain a temperature log.

The investigator must ensure safe storage of the investigational product to prevent loss, theft, or improper environmental conditions (temperature) specified by the Sponsor and described in the Investigator Brochure.

During the extension period from Week 54, BCD-085 will be given to the patients so that they can self-inject it at home. The investigational product should be transported by the patients in a cooling bag with additional cold packs to keep the temperature mode. The investigators should inform the patients that after arriving at home they should place the investigational product in the refrigerator (not in the freezer) at 2 to 8 °C; the investigational product must not be frozen. Guidelines on transportation, storage and use of the investigational product are given in the Patient’s Diary. Patients should be informed that they have to return a container with used syringes and cardboard cartons of the secondary packaging back to the study site during each visit. If there is no injection scheduled, the patient should return unused syringes. The investigator should check the amount of the investigational product used (and not used, if applicable).

#### **4.10. Procedure for code keeping and unblinding**

As this study is double-blind, the test product and placebo will be identified only by the patient-specific lot number. JSC BIOCADC will prepare envelop kits with therapy arm codes (i.e. with lot numbers corresponding to the test product/placebo). One of these envelop kits will be stored at JSC BIOCADC, another will be given to the principal investigator of every study site and stored in the Investigator’s File.

The investigator is allowed to unblind the treatment only in case of an emergency. The investigator must exercise his/her best efforts to prevent the loss or unblinding of study codes when unnecessary.

The treatment can be unblinded only in case of an emergency, when this is necessary to give an appropriate treatment to the patient and ensure his/her well-being. The investigator is allowed to unblind the treatment only in case of an emergency. The investigator must exercise his/her best efforts to prevent the loss or unblinding of study codes when unnecessary. In emergency cases, when urgent unblinding is required for the patient's benefit, the Investigator can unblind the treatment code first and then inform the representative of the Sponsor. After completing all necessary procedures, the Investigator should fill out the unblinding form and send it to JSC BIOCADC (to the Study Monitor, Drug Safety Division or Medical Expert) within 24 h from the moment when the code was unblinded. After unblinding, the Investigator should record this in the source documents.

At Week 12, the treatment will be unblinded by opening the randomization envelopes. This should be recorded in the primary documentation.

Each patient participating in the study will receive a Study Subject's Card, which will contain the Protocol title and code, study site number, and contact data of the Investigator. Patients should know that they should have their Study Subject's Cards all the time with them and notice medical personnel of any other medical facility about their participation in this clinical study. If necessary (for example, to administer another medicinal product), a healthcare professional of another medical facility (other than the study center) can contact the Investigator to discuss benefits or possible risks related to concomitant therapy.

#### **4.11. Data entered directly into CRF (i.e. no prior written or electronic record of data) and considered as source data**

All data to be recorded in the CRF should be present in the source documents of the study site.

In this study, no data will be entered directly to the CRFs without prior entering to the source documents.

### **5. ELIGIBILITY AND EXCLUSION OF STUDY SUBJECTS**

## 5.1. Inclusion criteria

1. Signed informed consent form (ICF).
2. Age of at least 18 years old at the time of signing the ICF.
3. Moderate to severe plaque psoriasis diagnosed at least 6 months before signing the ICF.
4. Patients who received at least one course of phototherapy or  systemic therapy for psoriasis or are candidates for such treatment according to the investigator.
5. Body surface area (BSA) affected by psoriasis of 10% or greater, the PASI score of 10 or greater, and the sPGA score of 3 or greater at screening.
6. Negative pregnancy urine test in female subjects (no test is required in women who are post-menopausal for at least 2 years and in surgically sterile women).
7. The ability of the patient (in the Investigator's opinion) to follow the Protocol procedures.
8. Patients of both sexes and their partners with reproductive potential must implement reliable contraceptive methods starting from signing the ICF to 20 weeks after the last dose of the investigational product. This requirement does not apply to patients after surgical sterilization and to females who are post-menopausal for 2 years or longer. Reliable contraceptive methods include one barrier method in combination with one of the following: spermicides, intrauterine device/oral contraceptives.

## 5.2. Exclusion criteria

1. Baseline erythrodermic, pustular, or guttate psoriasis or any other skin disorders (e.g. eczema) that can affect/complicate the assessment of psoriasis treatment.
2. Use of the following medications:
  - Prior exposure to any therapeutic monoclonal antibodies targeting IL-17 or its receptor;
  - Prior exposure to more than one drug containing monoclonal antibodies or their fragments;
  - Prior exposure to any monoclonal antibodies given within 12 weeks before signing the ICF;

---

 Systemic therapy refers to any non-biologics (methotrexate, cyclosporine, acitretin, mycophenolate mofetil, apremilast, calcitriol derivatives, etc.), or genetically engineered biologics (TNF inhibitors, anti-cytokine drugs, anti-CD20 drugs, etc.).

 BCD-085 is planned to be used as either a first- or second-line treatment, so the study involves treatment-naïve patients along with those who failed to respond to systemic therapy or phototherapy.

Translated from Russian to English, dated 26-Nov-2019

- Use of any systemic medications for the treatment of psoriasis (including glucocorticoids, methotrexate, sulfasalazine, cyclosporine, acitretin, mycophenolate mofetil, apremilast, calcitriol derivatives, etc.) within 4 weeks before signing the ICF. If these drugs were stopped less than 4 weeks before signing the ICF, the screening period should be extended up to 8 weeks during which no new systemic drugs are allowed;
- Use of phototherapy within 4 weeks before signing the ICF;
- Use of topical medications for the treatment of psoriasis within 2 weeks before signing the ICF;
- Vaccination with live or attenuated vaccines within 8 weeks before signing the ICF.

3. Any active systemic infection or recurrent infection at screening/randomization.
4. HIV, hepatitis B, hepatitis C, or syphilis.
5. Blood chemistry abnormalities appearing as:
  - a) creatinine  $> 2 \times$  upper limit of normal (ULN) at screening;
  - b) ALT, AST or alkaline phosphatase  $> 2.5 \times$  ULN at screening;
  - c) bilirubin  $> 1.5 \times$  ULN at screening;

---

 Except for NSAIDs.

 Patients may use topical glucocorticoids (of mild to moderate potency) on the face, underarm, and genitals. Patients may also use topical moisturizers, emollients, oils, and salicylic acid ointments, topical antibacterial and/or antimycotic agents as needed. Patients should discontinue all local skin products (medications or cosmetics) 24 hours before the planned PASI assessment.

 The screening for HBV includes tests for HBsAg and total antibodies to HBcor antigen (anti-HBcor total = IgG + IgM). If the test results for these markers (HBsAg and anti-HBcor total) are negative, the patient is considered eligible for the study by this criterion. If the patient tests positive for HBsAg, the patient cannot be included in the study regardless of the results for anti-HBcor. If the test results for HBsAg are negative but anti-HBcor total antibodies are detected, the patient should undergo an additional examination. The additional examination should include the following: qualitative PCR for HBV DNA, anti-HBcor IgM, and a consultation with the Infectious Disease Specialist. The activity of liver transaminases and concentration of bilirubin in blood chemistry results should be also considered. Having considered the examinations and test results, the Sponsor will decide whether to approve such a patient for the study. If it is known that the patient had hepatitis B infection in the past, an additional examination may be performed along with the main examination (blood samples for HBsAg, anti-HBcor total, anti-HBcor-IgM and blood samples for qualitative PCR to HBV DNA are taken on the same day).

The patient with anti-HCV antibodies can be included in the study if all of the following conditions are met: negative qualitative PCR results for HCV RNA (this test is performed only if anti-HCV antibodies are detected); no abnormalities (increased transaminases or bilirubin levels) found in blood chemistry; the Infectious Disease Specialist provides a documented conclusion that the patient has no HCV/cured HCV; and the Sponsor approves the enrollment of this patient. If it is known that the patient had HCV infection in the past, an additional examination may be performed along with the main examination (blood samples for anti-HCV and blood samples for qualitative PCR for HCV RNA are taken on the same day).

The patient who has a positive test for syphilis can be included in the study at the discretion of the Sponsor if the Dermatology/Venereology Specialist provides a documented report that the patient has no syphilis/cured syphilis. An additional examination may be required to confirm the diagnosis (at the discretion of the Dermatology/Venereology Specialist).

Translated from Russian to English, dated 26-Nov-2019

6. Leukocyte count  $< 3.0 \times 10^9/\text{L}$ ; absolute neutrophil count  $< 2.0 \times 10^9/\text{L}$ ; platelet count  $< 100 \times 10^9/\text{L}$ , or hemoglobin  $< 90 \text{ g/L}$  according to complete blood count at screening.
7. Any psychiatric conditions including severe depressive disorders and/or any history of suicidal thoughts or suicidal attempts.
8. Signs of clinically significant depression (Beck's score  $\geq 16$  at screening).
9. Alcohol or substance abuse.
10. Tuberculosis now or in the past.
11. Latent TB infection (positive results of the Diaskintest, QuantiFERON test, or T-spot).
12. Confirmed by source documentation and ongoing at screening, concurrent diseases that may increase the risk of adverse events during the study therapy or affect the evaluation of psoriasis symptoms (mask, enhance or alter the symptoms of psoriasis, or cause clinical or laboratory/instrumental symptoms similar to those of psoriasis):
  - Active inflammatory diseases or aggravation of chronic inflammatory diseases other than psoriasis;
  - Functional class III-IV stable angina of effort, unstable angina or a history of myocardial infarction within 1 year before signing the ICF;
  - Moderate to severe cardiac failure (NYHA class III-IV);
  - Treatment-resistant hypertension;
  - Severe asthma, a history of angioedema;
  - Moderate to severe respiratory failure, grade 3/4 chronic obstructive pulmonary disease;
  - Diabetes mellitus with inadequate glycemic control, i.e. if HbA1C level is  $\geq 8\%$  (to be valid, results should be obtained at screening or within 3 months before signing the ICF);

---

 This exclusion criterion can be confirmed or rejected on the basis of medical records or as told by the patient. Patient's medical history that can, in the opinion of the investigator, jeopardize the patient or affect his/her ability to follow the protocol must be carefully evaluated.

 TB diagnostics can be performed with the skin test (Diaskintest) or blood test (QuantiFERON/T-spot). QuantiFERON/T-spot can be repeated once. Upon reconciliation with the Sponsor, the patient with uncertain Diaskintest/QuantiFERON/T-spot results can be enrolled in the study if the TB Specialist confirms in written that the patient has no TB infection, and the patient shows no signs of active TB according to the chest X-ray performed any time within 3 months before signing the ICF or during the screening. The Diaskintest results are valid if the test was performed within 3 months before signing the ICF.

 Treatment-resistant arterial hypertension is defined as blood pressure above the target range despite the concurrent use of a combination of three anti-hypertensive drugs of different classes, necessarily including a diuretic, and non-medication methods (salt-free diet, controlled physical exercise).

 Glycated hemoglobin is measured only in patients with suspected/diagnosed diabetes mellitus.

- Thyrotoxicosis persisting despite thyrostatic drugs or hypothyroidism not compensated with thyroid hormone drugs;
- Systemic autoimmune diseases (including but not limited to systemic lupus erythematosus, rheumatoid arthritis, ankylosing spondylitis, Crohn's disease, non-specific ulcerative colitis, systemic scleroderma, inflammatory myopathy, mixed connective tissue disease, overlap syndrome, etc.);
- Any other underlying conditions (including but not limited to metabolism, hematology, renal, hepatic, pulmonary, neurological, endocrine, cardiac, and gastrointestinal disorders; infections) that, in the opinion of the Investigator, may affect the course of psoriasis, affect the assessment of its symptoms, or put the patient using the study therapy at unacceptable risk.

13. Malignancies with less than 5 years of remission.
14. Known severe allergies (anaphylaxis or drug allergy to two or more drugs).
15. Known allergy or intolerance to monoclonal antibody drugs (murine, chimeric, humanized, or fully human) or any other components of the test drug or comparator.
16. Major surgery within 30 days before the screening, or a major surgery being scheduled at any time during the study.
17. Severe infections (including those that required hospitalization or parenteral antibacterial/antimycotic/antiprotozoal agents) within 6 months before signing the ICF.
18. Use of systemic antibacterial/antimycotic/antiprotozoal agents within 2 months before signing the ICF.
19. More than 4 episodes of respiratory infections within 6 months before signing the ICF.
20. Episodes of systemic mycoses (histoplasmosis, coccidioidomycosis, blastomycosis, etc.) within 6 months before signing the ICF.
21. History of epileptic attacks or seizures.
22. Any concurrent diseases during which, in the Investigator's opinion, the study therapy can harm the patient.
23. Pregnancy, breastfeeding, or planning for pregnancy while participating in the study.

---

 In case of a history of thyroid disorders with thyrotoxicosis or hypothyroidism, the patient can participate in the study if he/she has laboratory confirmation of euthyroidism within 3 months before signing the ICF, and no symptoms developing during therapy with stable doses of antithyroid drugs/thyroid hormones for at least 4 weeks before signing the ICF.

 Signs/symptoms of psoriatic arthritis are not considered an exclusion criterion.

Translated from Russian to English, dated 26-Nov-2019

24. Participation in any other clinical study within 3 months before signing the ICF or simultaneous participation in other clinical studies.
25. Patients who have been already randomized in the study but then withdrawn due to any reasons cannot be included in the study.

### 5.3. Withdrawal criteria

The patient will be withdrawn from the study in the following circumstances:

1. Major violations of inclusion and/or exclusion criteria revealed after the enrollment (patients removed at the discretion of JSC BIOCAD).
2. The patient withdraws his/her consent to participate in the study.
3. The patient develops adverse events or serious adverse events, laboratory abnormalities or concomitant conditions that, in the investigator's opinion, make further participation in the study impossible, dangerous or non-beneficial regarding patient's well-being/safety.
4. During the main treatment period: The patient misses more than 2 injections (in this case, the patient's removal must be approved by JSC BIOCAD, refer to section 6.3.1. *Treatment compliance*) or misses 2 consecutive visits or 3 visits in total, or the patient regularly (7 times or more) violates the timing of the scheduled visits.
5. During the extension treatment period (Week 54 to Week 154 for patients from Arms 1 and 2, Week 54 to Week 166 for patients from Arm 3): If  $\geq 20\%$  injections are missed ( $\geq 5$  injections for patients initially randomized in Arms 1 or 2,  $\geq 6$  injections for patients initially randomized in Arm 3) or  $\geq 2$  consecutive visits/injections are missed;
6. The patient gets pregnant. If pregnancy is suspected, the urine test for HCG must be performed. If the test gives a positive result, the patient must be withdrawn from the study (follow-up procedures are described in section 5.4).
7. The patient is diagnosed with active tuberculosis during the treatment with the investigational product (the diagnosis should be confirmed by a documented impression from the TB Specialist);
8. The study is terminated by the decision of JSC BIOCAD, local ethics committees or regulatory authorities.
9. The patient uses medications prohibited by the Protocol.

---

 Violation of eligibility criteria justified by the investigator and approved by the Sponsor is not a reason for removing the patient from the study.

**The investigator must inform JSC BIOCADC within 24 h about the patient's premature withdrawal and specify the reason.**

**5.4. Follow-up of subjects withdrawn from the study or subjects who discontinued the study treatment but remain in the study for follow-up**

**5.4.1. Follow-up of patients who received at least one dose of the investigational product**

The following should be done if the patient who received at least one dose of the investigational product discontinues the study early:

- On the day of withdrawal, the Early Withdrawal Visit should be conducted and the investigator should complete the Early Withdrawal Visit and the End of Study forms in the eCRF. The Protocol does not specify the amount of procedures to be performed during the Early Withdrawal Visit; this is to be determined on a case-by-case basis.

Said procedures are mandatory for all subjects who prematurely withdrew from the study, except for the subjects who are lost to follow-up or are physically unable to attend the visit. All records must be supported with appropriate source documents.

If the subject discontinues the study due to an AE/SAE, the investigator should conduct further treatment and follow-up after the Early Withdrawal Visit in accordance with the study site standards for the treatment of a certain AE/SAE. The patient is to be **followed up until the AE or SAE resolves completely**.

If a woman involved in the clinical study or a partner of a clinical study participant becomes pregnant, this does not need to be reported as an AE unless the baby has any congenital abnormality or birth defect (these should be recorded as SAEs). However, all pregnancies must be documented in a Pregnancy Report Form and reported to the Sponsor as soon as possible. Women who discontinued the study because of becoming pregnant during the study should be monitored throughout the entire pregnancy and 6 months after childbirth to evaluate the mother's and child's health. Such monitoring is performed when possible and requires patient's consent for the pregnancy follow-up. Information on pregnancy course and outcome should be recorded in the source documentation (with consent from the patient).

Information about the health of the patient prematurely withdrawn from the study must be recorded in the source documentation and eCRF.

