Any other therapy during the study	Any medications other than the investigational product that are used to perform the study procedures. This includes, for example, the drugs used as part of the combination therapy.
Patient's premature withdrawal (dropout)	The time point when the patient discontinues the study before the planned completion of the study therapy and/or assessments. At this time point, the study therapy stops, and no further assessments are planned (follow-up for survival and/or disease progression may be an exception). If the patient discontinues the study due to an event planned by the Protocol (for example, a complete response), he/she is considered a dropout anyway.
Completion of the study	The time point corresponding to the final patient's visit.
Study therapy	Any medication or a combination of medications used in any arm as part of study procedures, including concomitant medications and introductory therapy before the active medication.
Concomitant therapy	Therapy with any drugs included in the study therapy, except for the test drug and reference drug. For example, drugs used for combination therapy, pre-medication etc.
Discontinuation of study therapy	Time point when the investigational therapy is terminated regardless of what caused the termination. It does not necessarily coincide with patient's withdrawal from the study.
Variable	An identifier used in data analysis; it is obtained directly or indirectly from data gained during the specified assessment within the specified time points.

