###### **6.1.2.1.1. Follow-up for toxicity**

In case of temporary or permanent treatment discontinuation, the patient should be followed up until the resolution or stabilization of the event. If the therapy is suspended for more than 14 days, it should be discontinued permanently. However, if the investigator and the Medical Expert believe that the patient who discontinued the drug for more than 14 days may get benefit from the therapy, the study treatment may be continued.

To reveal AEs and SAEs, all patients will be followed up for 28 days from the last dose of the investigational product.

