## **8.2. Methods and timeframes for assessment, documenting and analysis of safety variables**

### **8.2.1. Timeframes for analysis of safety variables**

Tolerability and safety endpoints will be analyzed at Weeks 12 and 54 of the study.

Information about serious adverse events will include data on SAEs developed from the time when the subject received the first dose of the investigational product until the time he/she completed the study (as planned or prematurely).

SAEs that developed during screening will be analyzed separately. Formally, these occurrences are not considered adverse events, because they develop before the administration of the investigational product. However, they can show the safety of screening procedures or be a reason to reject the patient during the screening, so they should be recorded.

The adverse events that do not meet the seriousness criteria should be recorded starting from the moment when the investigational product was injected the first time until the end of the Protocol-defined follow-up period after the patient stopped taking the investigational product (as planned or prematurely).

Drug Safety Division of JSC BIOCAD will analyze information about every SAE immediately after receiving an SAE report, provided that the investigator sent the report(-s) within the due time window. The cumulative analysis will be performed during the preparation of the final study report.

AEs not meeting the seriousness criteria will be analyzed routinely during the preparation of the final study report.

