### **8.2.2. Methods and timeframes for assessment and documenting of safety variables**

The safety analysis will include all patients who received at least one dose of the investigational product. Additionally, the SAE analysis will include all randomized patients starting from the ICF signing and until the end of their participation in the study.

Safety will be analyzed based on the information about

- AEs/SAEs,
- Physical examination data and vital signs,
- CBC, blood chemistry, and urinalysis results,
- ECG findings.

The frequency of these procedures is specified in section 4.6.1 “Schedule of study visits and procedures”. AEs/SAEs will be documented and reported in accordance with the Sponsor’s Manual.

The investigator is responsible for recording adverse events in the clinical study.

AEs are recorded beginning from the moment when the investigational product was injected the first time until the end of the follow-up period after the patient stopped taking the investigational product (as planned or prematurely). SAEs are recorded from the moment when the subject signed the informed consent form until the moment when he/she completed the study (as planned or prematurely). SAEs that were recorded during screening are not included in the total safety analysis. The Investigator can record an SAE later than stipulated by the Protocol if he/she believes that this SAE is related to the investigational product or study procedures.

An AE is considered to be resolved if the laboratory parameter, vital sign or symptom has returned to its baseline value. For all parameters, the baseline level is considered the value/sign severity that was seen in this patient before the first injection of BCD-085/placebo at the first scheduled visit per protocol. For AEs, including SAEs, of long-lasting/chronic nature, the resolution is the stabilization of the patient’s condition. For example, the AE “aggravation of chronic bronchitis” is considered to be resolved when the patient has achieved remission.

The Investigator must document non-serious AEs in the source documents and in the CRF, and show them to the Monitor at the next monitoring visit. Besides being recorded in the source documents and eCRF, serious adverse events (SAEs) must be reported to the Sponsor within 24 h in the SAE Report Form. SAE Report Forms must be sent to the Sponsor within 24 h by email to

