7. ANALYSIS POPULATIONS

Safety analysis

The safety analysis will include all patients randomized in the study (intent-to-treat (ITT) population).

Efficacy analysis

The efficacy will be assessed in the ITT (intent-to-treat) population, which includes all randomized patients. In addition, the efficacy can be evaluated in the PP (Per Protocol) population, which includes those patients who completed all visits without major protocol deviations.

Page 10 of 10

Immunogenicity analysis

The immunogenicity analysis will include all patients who have received at least one dose of BCD-085 and had an evaluable (not missing/lost/spoiled) serum sample taken before the first dose of BCD-085 and at least one evaluable (not missing/lost/spoiled) serum sample taken at subsequent visits.

Main demographics, baseline clinical and laboratory parameters obtained on the screening will be processed using descriptive statistics and will be analyzed in the efficacy and safety populations.

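### The protocol gives conflicting end dates for SAE capture after premature withdrawal, and sets no minimum assessments for the Early Withdrawal Visit

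*Protocol*

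**What the plan says.** Several parts of the protocol bear on what is collected once a patient leaves early.

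- **SAEs.** Section 8.2.1 includes SAEs in the analysis "until the time he/she completed the study (as planned or prematurely". Section 8.2.2 records them "until the moment when he/she completed the study (as planned or prematurely". It also allows the investigator to record a later SAE if he or she believes it is related to the product or to study procedures.
- **Non-serious AEs.** Section 8.2.1 records these "until the end of the Protocol-defined follow-up period after the patient stopped taking the investigational product (as planned or prematurely". Section 6.1 sets that follow-up at 4 weeks after the last injection.
- **Both together.** Section 6.1.2.1.1, with the stated aim of revealing AEs and SAEs, says that "all patients will be followed up for 28 days from the last dose of the investigational product".
- **Definitions.** Terms and Definitions equates completion of the study with the patient's final visit. It says that at premature withdrawal "the study therapy stops, and no further assessments are planned", apart from possible follow-up for survival or disease progression.
- **The withdrawal visit.** Section 5.4.1: "On the day of withdrawal, the Early Withdrawal Visit should be conducted", and the Early Withdrawal Visit and End of Study forms are completed. The visit is mandatory unless the patient is lost or physically unable to attend. On its content: "The Protocol does not specify the amount of procedures to be performed during the Early Withdrawal Visit"; this is settled case by case.
- **Other duties in 5.4.1.** A patient who leaves because of an AE or SAE is followed until it resolves. Information on a withdrawn patient's health must be recorded, with no content or duration given.
- **Immunogenicity population (SAP 7).** A patient needs a sample from before the first BCD-085 dose and "at least one evaluable (not missing/lost/spoiled) serum sample taken at subsequent visits".

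**The concern.** The sections that govern safety data give serious events an earlier closing date than non-serious ones in patients who leave early. Another section gives both the same 28 days. The tables of visits contain no contact that would carry out the 28-day rule in a withdrawn patient. The End of Study form is completed on the day of withdrawal, and the definition of withdrawal says no further assessments are planned.

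At stake is whether SAEs in the weeks after the last injection are collected in the same way at every site. The late-SAE allowance in 8.2.2 does not settle this. It permits recording but does not require it, and it depends on the investigator's view of causality, so SAEs judged unrelated can be missed.

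The open content of the Early Withdrawal Visit is a second and smaller matter. It leaves the last safety laboratory tests and the last antibody sample to individual choice.

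**Working it through.** **Step 1. Apply the rules to one patient.** Take a patient whose last dose is on day 0, who withdraws consent on day 10, and who has an event on day 20 that is judged unrelated.

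| Protocol source | Non-serious event, day 20 | Serious event, day 20 |
|---|---|---|
| 8.2.1 | in the window (to end of follow-up) | outside (window closed at premature completion, day 10) |
| 8.2.2, SAE sentence and late-SAE allowance | not addressed | outside; the allowance needs a view that it is related |
| 6.1.2.1.1 | in the window | in the window |
| Terms and Definitions | no assessment planned | no assessment planned |

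The day-10 closing date comes from combining two texts: completion is the final visit (Terms and Definitions), and a withdrawn patient's last visit is held on the day of withdrawal (5.4.1).

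**Step 2. Length of the gap.** Let *t* be the days from last dose to withdrawal. The period inside the 28 days of 6.1.2.1.1 but after SAE closure under 8.2 is

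gap = max(0, 28 − *t*) days.

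It is 28 days if withdrawal falls on a dosing day, 14 days if *t* = 14, and zero once *t* ≥ 28. A patient removed in the extension for missing two consecutive four-weekly injections is already 8 × 7 = 56 days past the last dose, so the gap is zero.

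**Step 3. Total.** The sample size section allows for 213 − 193 = 20 dropouts.

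- Upper bound: 20 × 28 = 560 patient-days.
- If every withdrawal came 14 days after the last dose (assumption): 20 × 14 = 280 patient-days.

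The 20 come from a calculation for the Week 12 endpoint. The documents give no expected number of withdrawals over the full 154 to 166 weeks; for *N* withdrawals the bound is 28 × *N* patient-days.

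**Step 4. Exposure in the gap.** The Phase I section gives a half-life of 15 to 22 days. With simple first-order decay (assumption), the fraction of a dose remaining is 0.5^(days/half-life):

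- day 14: 0.5^(14/15) = 0.52 to 0.5^(14/22) = 0.64;
- day 28: 0.5^(28/15) = 0.27 to 0.5^(28/22) = 0.41.

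This shows that drug is present during the gap. It does not measure events missed.

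**Step 5. Antibody sample.** Table 30 places the main-period samples at Weeks 0, 12, 24 and 54. A patient in Arm 1 or 2 who leaves before Week 12, with no sample at the Early Withdrawal Visit, has no later sample and drops out of the population in SAP 7.

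**The case against.** A reader might infer from 8.2 and the definition of withdrawal that safety collection stops when a patient leaves. The documents do not support that. Section 6.1.2.1.1 gives all patients 28 days for AEs and SAEs, 6.1 gives 4 weeks after the last injection, and 5.4.1 follows AE- or SAE-related withdrawals to resolution and requires health information on withdrawn patients.

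The withdrawal-day closing date is also an inference. Section 4.5 counts follow-up as part of participation. The AE sentence in 8.2.2 and the AE definition in 8.1.1.1 run to the end of follow-up and are not limited to non-serious events. Read with 6.1.2.1.1, the SAE window could include the 28 days. The definition of withdrawal looks like a generic glossary entry. This is a fair reading, but 8.2.1 separates serious from non-serious events and 8.2.2 gives SAEs their own end date. Two sites could reasonably act differently, and that is the defect.

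A reader might also infer that the Early Withdrawal Visit requires nothing. That is too strong: 8.3.1 calls for an AE record at every visit, and the visit and its forms are mandatory. The eCRF form is not available here and may ask for more. What is missing is a stated minimum of assessments.

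Week 52 PASI 75 non-responders might seem a large second group leaving before the Week 54 tests. In the Visit 22 list, however, only training, self-injection and dispensing (of product and diary) depend on entering the extension. The antibody sample, chemistry, ECG and TB test do not. Week 54 is (54 − 50) × 7 = 28 days after the Week 50 dose. Nor do the documents point to a large group: the Phase II extension reports 98.06% PASI 75 at one year, and 213 × (1 − 0.9806) is about 4 patients, although that study enrolled Phase II completers on somewhat different regimens.

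On immunogenicity, requiring a later sample is an ordinary evaluability rule, and the four completed BCD-085 patient studies reported no binding antibodies. On efficacy, a withdrawal-day PASI would not supply the Week 12 endpoint, since missing data are not replaced. Both arguments stand and keep the second point small.

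**Conclusion.** The contradiction on SAE capture is real. Sections 8.2.1 and 8.2.2 close the SAE window at premature completion, 8.2.1 keeps non-serious AEs open through follow-up, 6.1.2.1.1 keeps both open for 28 days, and the definition of withdrawal plans no further assessments. The late-SAE allowance does not repair this, because it is optional and limited to events judged related.

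The effect is bounded. It concerns withdrawn patients only, 0 to 28 days each, and at most 560 patient-days on the planning figure of 20 dropouts. That figure assumes that every dropout leaves on a dosing day and can still be contacted. It could be exceeded if more patients withdraw over three years.

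The missing minimum set at the Early Withdrawal Visit is secondary. Its clearest consequence is that a BCD-085 patient who leaves before any post-baseline sample is lost to the immunogenicity analysis. The point merits correction at moderate priority and does not threaten the primary analysis.

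**What to change.** 1. **One end date.** Reconcile Terms and Definitions, 6.1.2.1.1, 8.2.1 and 8.2.2 so that, in prematurely withdrawn patients, SAE capture ends no earlier than non-serious AE capture. That is the 28 days after the last dose already stated in 6.1.2.1.1, whatever the investigator's opinion on causality. The allowance for later related SAEs can remain for events beyond that date.
2. **A contact to carry it out.** Add a phone contact at 28 days after the last dose if no visit falls then, subject to the patient's consent.
3. **A minimum set in 5.4.1.** Replace the case-by-case sentence with at least AE/SAE review, the laboratory safety tests and the antibody sample. PASI may be added as supportive data only.
4. **A clarifying sentence.** State that Week 52 PASI 75 non-responders attend Visit 22, as the visit list already implies.

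The cost is a protocol amendment, an eCRF page built from existing forms, and for each withdrawn patient one set of routine assessments and at most one phone call. Patients lost to follow-up will still be missed.
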